5.5 Patient Input on Study Design

Patient input was obtained for this study in various international regions. Patients were able to understand and comment on the requirements for study participation.

6. Study Population

Screening: Investigators will be expected to maintain a screening log of all potential study candidates that includes limited information about the potential candidate (eg, date of screening). This log may be completed and updated via an Interactive Response Technology (IRT) system. Eligibility criteria will be evaluated at screening visit and at baseline/day 1 visit, prior to randomization.

[figure not shown]
The screening visit will confirm all eligibility requirements described in Section 6.1 and 6.2 and [Table 2-1](#). All SLE-related screening criteria will be reviewed by the adjudication team. The site will be notified by electronic communication of the results of this review and baseline/visit 1 should not occur prior to this notification. Subjects who do not meet the eligibility criteria will be considered screen fails but may be eligible for rescreening as described in Section 9.1.1.

The baseline/day 1 visit will occur up to 33 calendar days following the screening visit (it can be earlier if all eligibility requirements for screening visit are met). Baseline/day 1 visit will confirm eligibility requirements prior to randomization, as described in Section 6.3. Subject who meet all eligibility criteria may proceed to randomization and dosing. Subjects who do not meet criteria may be eligible for rescreening as described in Section 9.1.1.

Before any study-specific activities/procedures, the appropriate written informed consent must be obtained (see Section 12.3).

Prospective approval of protocol deviations to recruitment and enrollment criteria, also known as protocol waivers or exemptions will not be provided.

Figure 6-1. Screening and Enrollment

PD = pharmacodynamic; PK = pharmacokinetic; SLE = systemic lupus erythematosus

6.1 Inclusion Criteria Screening Visit

Subjects are eligible to be included in the study only if all the following criteria apply:

- 101 Subject has provided informed consent prior to initiation of any study-specific activities/procedures.
- 102 Age ≥ 18 years to ≤ 75 years at screening visit.
- 103 Fulfills classification criteria for SLE according to the 2019 European League Against Rheumatism (EULAR)/American College of Rheumatology (ACR) classification criteria for SLE (Aringer et al, 2019), with antinuclear antibody $\geq 1:80$ by immunofluorescence on Hep-2 cells being present at screening.
- 104 Hybrid SLEDAI score ≥ 6 points with a "Clinical" hSLEDAI score ≥ 4 points.

The "Clinical" hSLEDAI is the hSLEDAI assessment score without the inclusion of points attributable to laboratory results, including urine or immunologic parameters.

Additional protocol-specific rules are applied at screening and throughout the study, as follows:

- Arthritis: Arthritis (at least 3 tender and swollen joints) must involve joints in the hands or wrists for the hSLEDAI scoring.
- Alopecia: Subjects should have hair loss without scarring; should neither have alopecia areata nor androgenic alopecia; and should have a CLASI activity score for alopecia ≥ 2 .
- Oral ulcers: Ulcers location and appearance must be documented by the investigator.
- Scleritis and Episcleritis: the presence of stable SLE-related scleritis and episcleritis (ie, that will likely not require initiation/increase in immunosuppressants/immunomodulators as outlined in the

inclusion/exclusion criteria) must be documented by an ophthalmologist and other causes excluded.

- Renal: subjects with urine protein/creatinine ratio $< 3000 \text{ mg/g}$ (or equivalent method) in a clear catch spot urine sample can enroll and be scored in the hsLEDAI, provided the subject has a clinical hsLEDAI ≥ 4 and did not receive induction treatment for nephritis within the last year.
- Pleurisy and Pericarditis: symptoms of pleurisy and pericarditis must be accompanied by objective findings to be scored in the hsLEDAI.

105 Unless there is a documented intolerance, **subjects** must be taking:

- **Only 1** of the following SLE treatments: anti-malarial (hydroxychloroquine, chloroquine, or quinacrine), azathioprine, methotrexate, **leflunomide**, mycophenolate mofetil/acid mycophenolic, or dapsone.

OR

- 2 of the above-mentioned SLE treatments in which 1 must be **anti-malarial** (hydroxychloroquine, chloroquine, or quinacrine).

Treatment should be taken for ≥ 12 weeks prior to screening and must be a stable dose for ≥ 8 weeks prior to screening.

106 For subjects taking OCS, dose must be $\leq 20 \text{ mg/day}$ of prednisone or OCS equivalent, and the dose must be stable at baseline visit for ≥ 2 weeks prior to screening visit.

6.2 Exclusion Criteria Screening Visit

Subjects are excluded from the study if any of the following criteria apply:

Disease Related

201 Urine protein creatinine ratio $\geq 3000 \text{ mg/g}$ (or equivalent) at screening or induction therapy for lupus nephritis within 1 year prior to screening visit.

202 Active CNS lupus within 1 year prior to screening including, but not limited to, aseptic meningitis, ataxia, CNS vasculitis, cranial neuropathy, demyelinating syndrome, optic neuritis, psychosis, seizures, or transverse myelitis.

Other Medical Conditions

203 Diagnosis of any inflammatory joint or skin disease other than SLE (confirmed accurate by the PI) currently present or within 1 year prior to screening which would interfere with SLE disease assessment based on investigator judgment.

204 Any disease other than SLE that has required treatment with oral or parenteral **CS** for > 2 weeks within 6 weeks prior to screening.

205 Active infection (including chronic or localized infections), **OR infection** for which anti-infectives were **initiated** within 4 weeks prior to screening OR presence of serious infection, defined as requiring hospitalization or **IV** anti-infectives within 8 weeks prior to screening.

206 Active tuberculosis or latent tuberculosis with no documented past history of adequate treatment per local standard of care.

207 Positive test for tuberculosis during screening defined as: either positive or indeterminate QuantiFERON®-TB OR T-spot test OR positive purified protein derivative (PPD) (≥ 5 mm of induration at 48 to 72 hours after test is placed).

- Subjects with a positive PPD and a history of Bacillus Calmette-Guérin vaccination are allowed to enroll with a negative QuantiFERON®-TB or T-Spot test.
- Indeterminate QuantiFERON®-TB or T-spot test can be repeated once, based on investigator judgment. Subjects can enroll if second result is negative. Subjects with persistent indeterminate or positive test results should proceed as below.
- Subjects with a positive PPD test (without a history of Bacillus Calmette-Guérin vaccination) or a positive or indeterminate QuantiFERON®-TB or T-Spot test (including repeated results when performed) are allowed to enroll if they meet ALL the following criteria at screening:
 - no symptoms per tuberculosis worksheet provided by Amgen
 - documented history of adequate TB treatment or prophylactic treatment for latent TB (completed per local standard of care prior to the start of investigational product)
 - no known exposure to a case of active tuberculosis after most recent treatment/prophylaxis
 - chest X-ray with no new radiographic findings suggestive of active TB (to be read by local facility)

Note: 1) these tests do not need to be repeated at the time of rescreening, unless rescreening occurs ≥ 12 months from screening visit or subject's medical/epidemiologic history suggests newly acquired infection or recent contact with TB cases and 2) repeat testing of an indeterminate QuantiFERON test using the T-spot test may be performed.

208 Positive for hepatitis B surface antigen (HBsAg); or positive for hepatitis B core antibody (HBcAb) in the presence of detectable viral DNA in peripheral blood, assessed by polymerase chain reaction (PCR). Subjects positive for HBcAb without detectable viral DNA by PCR are allowed to enroll, provided the subject undergoes monitoring of viral DNA by PCR at **approximately** every 3 months during the treatment period, up to **a minimum of** 16 weeks after **last administration of the investigational product**. If viral DNA becomes detectable during the study period, the subject should be evaluated by an hepatologist before stopping the treatment to evaluate the need to start specific hepatitis B treatment before investigational product discontinuation. A history of hepatitis B vaccination without history of hepatitis B infection (ie, positive hepatitis B surface antibody (HBsAb), negative HBsAg and negative HBcAb) is allowed.

Positive for hepatitis C antibody in the presence of detectable viral ribonucleic acid (RNA) in peripheral blood, assessed by PCR. Subjects positive for hepatitis C antibody without detectable viral RNA by PCR are allowed to enroll, provided the subjects undergo monitoring of viral RNA by PCR at **approximately** every 3 months during treatment period up to a **minimum of** 16 weeks after **last administration of the investigational product**. If viral RNA become detectable during the study period, the subject should be evaluated by an hepatologist before stopping the treatment to evaluate the need to start specific hepatitis C treatment before investigational product discontinuation.

Note: these tests do not need to be repeated at the time of rescreening, unless rescreening occurs \geq 12 months from screening or there is evidence or suspicion of recent infection.

209 Known history of HIV or positive serology for HIV antibodies at screening.

Note: these tests do not need to be repeated at the time of rescreening, unless rescreening occurs \geq 12 months from screening or there is evidence or suspicion of recent infection.

210 Presence of 1 or more significant concurrent medical conditions per investigator judgment, including but not limited to the following:

- poorly controlled diabetes or hypertension
- symptomatic heart failure (New York Heart Association class III or IV)
- myocardial infarction or unstable angina pectoris within the past 12 months prior to screening
- severe chronic pulmonary disease requiring oxygen therapy
- multiple sclerosis or any other demyelinating disease
- major chronic inflammatory disease or connective tissue disease other than SLE (eg, RA, Primary Sjogren Syndrome, Mixed Connective Tissue Disease)

Note: Subjects with positive antiphospholipid antibodies or diagnosis of antiphospholipid antibody syndrome according to the revised Sapporo classification criteria (Miyakis et al, 2006) can enroll in the study provided they have no current or past history of thrombotic events and meet all the other eligibility criteria.

211 Any history of malignancy with the following exceptions:

- resolved non-melanoma skin cancers $>$ 5 years prior to screening
- resolved cervical carcinoma $>$ 5 years prior to screening
- resolved malignant colon polyps $>$ 5 years prior to screening

Prior/Concomitant Therapy

212 Currently receiving or had treatment with: cyclophosphamide, chlorambucil, nitrogen mustard, or any other alkylating agent within 6 months prior to

screening; sirolimus or oral calcineurin inhibitors (eg, cyclosporine, tacrolimus, voclosporin) **or thalidomide** within 4 weeks prior screening.

213 Currently receiving or had treatment with a **Janus kinase (JAK)** inhibitor within 1 month prior to screening.

214 Currently receiving or had treatment with an immune checkpoint inhibitor (eg, PD-1 inhibitor, PD-L1 inhibitor, CTLA-4 inhibitor).

Note: Abatacept is not considered a CTLA-4 inhibitor and is referred to below.

215 Current or previous treatment with a biologic agent **with immunosuppressive/immunomodulatory activity** for SLE or other conditions as follows: rituximab within 6 months prior to screening; **abatacept**, belimumab, and anifrolumab within the past 3 months prior to screening; other biologics within less than 5 drug half-lives **or within the period of pharmacodynamic activity, when relevant**, prior to screening.

216 Subjects who have received intra-articular, intra-lesional, or systemic corticosteroid injections within 6 weeks prior to screening.

217 Subjects who have received live vaccines within 5 weeks prior to screening, or plan to receive live vaccines during the treatment period and up to 16 weeks after **last administration** of the **investigational product**.

Prior/Concurrent Clinical Study Experience

218 Currently receiving treatment in another investigational device or drug study.

219 Ending a treatment with an investigational drug or investigational device less than 5 **drug** half-lives from the last dose of the investigational **product or within the period of its pharmacodynamic activity when relevant**, at screening.

220 Subject previously randomized in this study.

Diagnostic Assessments

221 Presence of laboratory abnormalities at screening including the following:

- Aspartate aminotransferase (AST) or alanine aminotransferase (ALT) > 2 x upper limit of normal (ULN)
- Serum total bilirubin (TBL) \geq 1.2 mg/dL (\geq 26 μ mol/L) **except for Gilbert's Syndrome**
- Hemoglobin < 8 g/dL (< 80 g/L)
- Platelet count < 75,000/mm³ (75×10^9 /L)
- White blood cell count < 2000 cells/mm³ (2×10^9 /L)
- Absolute neutrophil count (ANC) < 1,000/mm³ (1×10^9 /L)
- Calculated glomerular filtration rate of \leq 30 mL/min/1.73 m² using the Modification of Diet in Renal Disease (MDRD) formula

222 Any other laboratory abnormality, which in the opinion of the investigator or Central Review Team, poses a safety risk, will prevent the subject from completing the study or will interfere with the interpretation of the study results, or might cause the study to be detrimental to the subject.

Other Exclusions

223 Female subject is pregnant or breastfeeding or planning to become pregnant or breastfeed during treatment and for at least 10 additional weeks after the last dose of investigational product.

224 Female subjects of childbearing potential unwilling to use 1 highly effective method of contraception during treatment and for at least 10 additional weeks after the last dose of investigational product administration. Refer to Section 12.5 for additional contraceptive information.

225 Female subjects of childbearing potential with a positive pregnancy test (serum pregnancy test **required** at screening, and urine pregnancy test **required** at day 1 visit).

226 Subject has known sensitivity to any of the products to be administered during dosing.

227 Subject likely to not be available to complete all protocol-required study visits or procedures, and/or to comply with all required study procedures (eg, Clinical Outcome Assessments) to the best of the subject and investigator's knowledge.

228 History or evidence of any other clinically significant disorder, condition or disease (with the exception of those outlined above) that, in the opinion of the investigator or Central Review Team would pose a risk to subject safety or interfere with the study evaluation, procedures, or completion.

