Once the subject is registered as rescreened, a new 33-day screening window will begin. All procedures noted in Section 6, including the informed consent and all laboratory parameters (Section 9.2.4) must be repeated with the following exception:

- tuberculosis screening tests (QuantiFERON®-T, T-spot test OR PPD), serologies for hepatitis B virus, hepatitis C virus and HIV may not be repeated provided that rescreening occurs ≤ 12 months of screening visit (**where those test results were negative**) and there is no patient's medical/epidemiological history suggestive of infection or recent exposure to cases of infection.

Screen fail subjects may be eligible for re-screening up to 2 times.

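### The note to exclusion criterion 208 can be read to waive a repeat viral PCR at rescreening in hepatitis antibody-positive subjects, where Section 9.1.1 requires one: a minor subject-safety inconsistency

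*Protocol*

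**What the plan says.** Criterion 208 (Protocol Section 6.2) covers hepatitis B surface antigen, hepatitis B core antibody, hepatitis B DNA by PCR, hepatitis C antibody and hepatitis C RNA by PCR. For two groups the PCR decides eligibility: "Subjects positive for HBcAb without detectable viral DNA by PCR are allowed to enroll", and "Subjects positive for hepatitis C antibody without detectable viral RNA by PCR are allowed to enroll", in both cases subject to PCR monitoring on study. Section 9.2.4.4 likewise makes a negative PCR at screening a condition of entry for these subjects.

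The note that closes the criterion reads "Note: these tests do not need to be repeated at the time of rescreening, unless rescreening occurs" at or after the 12-month mark. Its only other trigger for repetition is a recent infection that is evident or suspected.

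Sections 6, 6.4 and 6.5 send the reader to Section 9.1.1 for rescreening. That section says "Once the subject is registered as rescreened, a new 33-day screening window will begin" and then "All procedures noted in Section 6, including the informed consent and all laboratory parameters (Section 9.2.4) must be repeated with the following exception". The exception is that tuberculosis tests and "serologies for hepatitis B virus, hepatitis C virus and HIV may not be repeated provided that rescreening occurs" at ≤ 12 months, the earlier results were negative, and nothing in the history suggests infection or recent exposure. Viral PCR is not in that list.

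**The concern.** Both texts tell a site what to redraw when a subject is screened a second or third time, and they differ. The note speaks of the tests in its criterion without limit, and in that criterion PCR is the deciding test for antibody-positive subjects. It also carries no requirement that the earlier result was negative. Section 9.1.1 limits its waiver in both respects.

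The note stands inside the exclusion criterion, where a site checks eligibility, so a site could act on it without turning to 9.1.1. The subjects at issue have evidence of past hepatitis B or C and are about to start an investigational immunomodulator. The criterion itself foresees virus appearing in hepatitis B core antibody-positive subjects: "If viral DNA becomes detectable during the study period, the subject should be evaluated by an hepatologist". What is at stake is how recent the negative PCR is when such a subject is randomized.

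**Working it through.** There is no planned figure to reproduce. The check compares the two texts case by case and then bounds the age of the PCR.

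**Step 1: compare the instructions.** Take a rescreening before 12 months with no sign of recent infection or exposure.

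| Earlier result | Note to 208 | Section 9.1.1 | Agreement |
|---|---|---|---|
| All serologies negative | Waives the tests; PCR never triggered | Waives serology; PCR never triggered | Agree |
| HBcAb or hepatitis C antibody positive, PCR undetectable | Can be read to waive serology and PCR | Serology repeated (earlier result not negative); PCR repeated (not in the exception) | Conflict |
| HBsAg positive or PCR detectable | Waives the tests; the earlier excluding result stands | All repeated | Differ, but the note lets no one in |

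Only the second row carries a risk. PCR falls under the repeat rule in 9.1.1 for two reasons. It belongs to Section 9.2.4 (through 9.2.4.4), and Table 12-1 lists viral DNA and RNA as their own tests, triggered by the antibody result.

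**Step 2: bound the age of the PCR at randomization.**

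Inputs:
- Longest time from start of screening to randomization: 33 days (Section 5.1; Table 2-1 footnote d).
- Latest rescreening at which the note still waives: just under 12 months, taken as day 364.
- Assumption: the PCR was drawn at the screening from which the 12 months are counted.

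Under 9.1.1, the new PCR falls in the new window, so its age is at most 33 days.

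Under the note, the longest age is 364 + 33 = 397 days, and 397 × 12/365 = 13.05 months, or about 13 months.

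These are upper limits. The documents give no distribution of rescreening intervals and no count of rescreened antibody-positive subjects, so neither a typical age nor the number affected can be calculated.

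**Step 3: the boundary.** The note requires repetition at ≥ 12 months and 9.1.1 waives at ≤ 12 months. At exactly 12 months both apply, with opposite results. This is one point on the scale, but it sits in the same sentence that needs rewording.

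**The case against.** The strongest reply is that the documents already settle the matter. The note is permissive and 9.1.1 is mandatory, so a site that repeats the PCR satisfies both. Sections 6, 6.4 and 6.5 all defer to 9.1.1. Amendment 3, item 20, records the negative-result condition as a deliberate clarification, so the note is best seen as text that was not brought into line. The note never names PCR, and the same sentence closes criterion 209, where HIV serology is the only test. A serology-only reading is therefore available.

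Most of this stands. It shows what the sponsor intended and which section prevails. It does not remove the mismatch: the note is part of the current protocol, it follows a criterion that turns on PCR, and it gives a site a reason not to draw the test.

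The safeguards also stand. Section 9.1.1 requires liver tests again at rescreening, and criterion 221 excludes AST or ALT above 2 × ULN and raised bilirubin (except in Gilbert's syndrome). Criteria 222 and 228 let the investigator or Central Review Team exclude on judgment. On treatment, PCR is done about every 3 months (Table 2-1 footnote g), and the hepatotoxicity rules of Appendix 7 apply.

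A reader might infer three stronger things that the documents do not support:
- **That the protocol drops the PCR for these subjects.** It does not; 9.1.1 requires it.
- **That the PCR would always be at least some weeks old under the note.** Appendix 3 contemplates rescreening within 33 days of the previous consent signature, so no firm minimum age follows.
- **That a subject would receive several doses before any further PCR.** Part of Table 2-1 is not legible in the available text, and Table 2-2 footnote c dates monitoring from baseline. A day 1 PCR can be neither confirmed nor ruled out.

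**Conclusion.** The inconsistency holds as a minor subject-safety point of the lowest severity. For a rescreened subject who is HBcAb or hepatitis C antibody positive with an earlier undetectable PCR, the note can be read to waive a test that 9.1.1 requires. Followed literally, the note allows a PCR of up to about 13 months at randomization instead of at most 33 days.

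This rests on reading the note's reference to tests as including PCR, which the wording permits but does not compel. The number of subjects is unknown, probably small, and could be zero. The point has no bearing on power, type I error or the primary estimand. SAP Section 3.1 records that enrollment was stopped for futility, so nothing in the conduct of this trial would change.

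**What to change.** Reword the note to criterion 208 so that it matches 9.1.1:
- Waive repetition only for hepatitis B and C serologies that were negative.
- State that subjects positive for HBcAb or hepatitis C antibody need a new negative viral DNA or RNA PCR in each rescreening window.
- Use one boundary in the note and in 9.1.1: repeat at ≥ 12 months, waive at < 12 months.

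Matching edits to the notes under criteria 207 and 209 are optional, for consistency.

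The cost is one reworded note and one changed symbol. The repeat PCR adds no new burden, because 9.1.1 already requires it. With enrollment closed, the wording should be carried into later protocols that reuse this text.

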6.3 Inclusion Criteria Baseline/Day 1 Visit

Baseline/day 1 visit should occur after confirmation of SLE-related eligibility by the adjudication team and up to 33 days after screening visit. At baseline/day 1 visit, the following 2 criteria should be assessed prior to randomization:

107 Stability of SLE treatments: OCS and other immunosuppressants/immunomodulators doses must be stable since screening visit, by reviewing subject's medication history.

108 Disease activity: active disease as indicated by clinical hSLEDAI score ≥ 4 must be observed (clinical hSLEDAI score is the hSLEDAI assessment score without the inclusion of points attributable to laboratory results).

